- Serious adverse event, adverse event, laboratory abnormality of considerable clinical concern or considerable worsening of the subject's clinical symptoms
- At the specific request of the sponsor and in liaison with the investigator (e.g. obvious non-compliance, safety concerns).
- Return of heavy menstrual bleeding, if it affects the subject's well-being, based on the investigator's clinical judgment

The reasons for any withdrawal are to be fully documented on the eCRF.

End of treatment visit (Visit 8) and the end of study phone call (3 weeks after the Mirena removal) must be performed also for all subjects discontinuing the study prematurely.

Depending on the time point of withdrawal, a withdrawn subject is referred to as either "screening failure" or "dropout" as specified below:

Screening failure

A subject who, for any reason (e.g. failure to satisfy the entry criteria), terminates the study before the time point used for the definition of "dropout" (i.e. before completion of the baseline visit, Visit 2) is regarded a "screening failure".

Re-starting the defined set of screening procedures to enable the "screening failure" subject's participation at a later time point is not allowed – with the following exceptions:

- Initial screening occurred too early, i.e. before 4 years and 6 months of the Mirena use
- The in- / exclusion criteria preventing the subject's initial attempt to participate have been changed (via protocol amendment).

In any case, the investigator has to ensure that the repeated screening procedures do not expose the subject to an unjustifiable health risk. Also, for re-screening, the subject has to re-sign the informed consent form, even if it was not changed after the subject's previous screening.

Dropout

A subject who discontinues study participation prematurely for any reason is defined as a "dropout" if the subject has already been deemed eligible to participate and completed the baseline visit (visit 2).

General procedures

In all cases, the reason for withdrawal must be recorded in the eCRF and in the subject's medical records.

The subject may object to the generation and processing of post-withdrawal data as specified in Section 13.4.

Any subject removed from the trial will remain under medical supervision until discharge or transfer is medically acceptable.

Details for the premature termination of the study as a whole (or components thereof) are provided in Section 12.

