10.3.2.2 Analysis of the secondary variables

10.3.2.2.1 Menstrual blood loss

This section was changed in Amendment 1, see Section 15.1.1.10.

Menstrual blood loss (MBL) at beginning of year 6, end of year 6, end of year 7, and end of year 8 of Mirena treatment will be presented by descriptive statistics. Furthermore, change from baseline (=beginning of year 6) will be presented.

The basis for this analysis is the data on MBL assessed by the alkaline hematin method (see section 9.4.2). If a woman has documented in the eDiary (see section 9.7.1) that no bleeding occurred during one of the 30-day time periods considered for collection of sanitary products, the MBL will be assumed to be zero in that time period. The handling of partial or missing data (i.e. data on sanitary products and/or bleeding intensities) and detailed imputation rules will be described in the statistical analysis plan.

This analysis will be conducted in the FAS in the HMB subgroup, i.e. women who had Mirena inserted for both contraception and HMB.

CCI

CCI [REDACTED]

[REDACTED]

[REDACTED]

[REDACTED]

- [REDACTED]
- [REDACTED]

[REDACTED]

[REDACTED]

- [REDACTED]
- [REDACTED]

[REDACTED]

[REDACTED]

- [REDACTED]
- [REDACTED]
- [REDACTED]

[REDACTED]

[REDACTED]

- [REDACTED]
- [REDACTED]
- [REDACTED]

CCI [REDACTED]

- [REDACTED]
- [REDACTED]
- [REDACTED]
- [REDACTED]

[REDACTED]

- [REDACTED]
- [REDACTED]
- [REDACTED]
- [REDACTED]

Success will be concluded regarding this endpoint if less than 20% of the women in the HMB subgroup have a clinical change in bleeding profile regarding HMB (according to the definition above) and the upper limit of the corresponding 95% Clopper-Pearson confidence interval is equal to or less than 35%.

This analysis will be conducted in the FAS in the HMB subgroup, i.e. women who had Mirena inserted for both contraception and HMB.

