The target for the total number of women to be included in the extended treatment period is 360 women (200 women to complete study treatment). To evaluate the effect of extended Mirena use on HMB, it is targeted that 10% of the women to be treated (i.e. 36 women out of 360) should have Mirena prescribed for the treatment of HMB in addition to contraception. Please note subjects who have Mirena prescribed for contraception and HMB will have to consent to the HMB subgroup procedures.

The study will consist of a screening, treatment, and a follow-up period. Screening can be started when the subject has had the Mirena in place for 4 years and 6 months. Screening activities should be completed within 60 days after signed informed consent to allow enough time for the evaluation of the subjects’ eligibility to the study. Baseline visit (Visit 2) will be scheduled to take place 0 to 14 days before the end of Year 5 of Mirena use; and this is the start of the ‘treatment period’. The ‘treatment period’ is defined as the 3-year period following the baseline visit, whereas the ‘extension treatment period’ is defined as the 3-year period following Day 1 of Year 6 of Mirena use, i.e. Years 6, 7 and 8 of extended use of Mirena (refer to Section 4.1.1 for further details).

Analyses of the efficacy and safety data will be conducted after all subjects have either completed 6 and 7 years of treatment, respectively, or prematurely terminated their study participation before this time point.

Final analysis will be done after all subjects have either completed 8 years of treatment or prematurely terminated their study participation.

4. General Statistical Considerations

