4.4 Handling of Missing Bleeding Intensities and Censored eDiaries

Uterine bleeding data will be handled according to the sponsor's BPD "Recording and evaluation of bleeding data" (RD-SOP-1107) (1).

Up to two consecutive days of missing bleeding intensities will be replaced using a worst case approach during the evaluations. That is, the missing bleeding intensity will be replaced by the maximum of the bleeding intensities of the day before and the day after the missing day(s). If three or more consecutive days are missing bleeding intensities, the entire reference period is to be considered invalid/missing for the analyses.

Up to five days of missing bleeding intensities per 90-days reference period will be replaced. If more than five days are missing bleeding intensities, the entire 90-days reference period is to be considered invalid/missing for the analyses.

Up to two days of missing bleeding intensities per 28-days reference period will be replaced. If more than two days are missing bleeding intensities, the entire 28-days reference period is to be considered invalid/missing for the analyses.

A diary that ends before the end of the reference period will still be evaluated if it is at least two thirds of the length of the reference period. The bleeding pattern indices incorporating the length of an event, such as mean length of the bleeding episodes, will be calculated as for a complete diary. However, the bleeding pattern indices incorporating the number of days or the number of events will be corrected in order to account for the shorter length of the diary. The correction factor is the length of the reference period divided by the length of the diary. For example, 15 days of bleeding recorded in the diary that was kept 75 days instead of the 90 days of the entire reference period will be adjusted to $15 \times (90 / 75) = 18$ days. This rule assumes that the observed average number of bleeding days ($15 / 75$) stays constant in the reference period ($15 / 75 = 18 / 90$).

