6.2.2 Secondary efficacy variables

6.2.2.1 Menstrual blood loss

Subjects in the HMB subgroup are requested to collect their used sanitary products during four periods of 30 days each, as described in Integrated Protocol Section 9.1 and Integrated Protocol Table 9–2, i.e. for the following study days:

- beginning of Year 6, i.e. 30 days after baseline visit = study days 2-31
- end of Year 6, i.e. 30 days prior to Visit 4 (-14 days) = study days 322-351
- end of Year 7, i.e. 30 days prior to Visit 6 (-14 days) = study days 687-716
- end of Year 8, i.e. 30 days prior to Visit 8 (-14 days) = study days 1052-1081

MBL data will be available per HMB subject per collection period per day per sanitary product. MBL data from sanitary products collected during these planned 30-day collection periods will be included in the statistical analysis; potential additional MBL data from sanitary products collected outside these planned 30-day collection periods will be excluded from the statistical analysis.

Since MBL is related to the bleeding intensity, missing MBL data during the planned 30-day collection periods will be imputed depending on the subject's daily bleeding intensity recorded in the eDiary, as described in Section 4.5.

The cumulative volume of MBL will be calculated only if a day-wise cumulative MBL (original or imputed value, as described in Section 4.5 and Table 4–1) is available for each day in the planned 30-day collection period (or until the day of premature discontinuation). Otherwise, the collection period will be considered invalid and the cumulative volume of MBL will not be calculated.

If there are less than 20 solid observations in a planned 30-day collection period (“solid” as defined in Section 4.5 and Table 4–1), the collection period will be considered invalid and the cumulative volume of MBL will not be calculated. This rule also applies to HMB subjects who discontinued prematurely during a 30-day collection period, i.e. if there are less than 20 solid observations before the subject discontinued prematurely during a 30-day collection period, the collection period will be considered invalid and the cumulative volume of MBL will not be calculated.

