The cumulative volume of MBL will be calculated per HMB subject per analysis period as the sum of MBL values, adjusted for the length of the analysis period (in case of early and/or late collection without gap, and/or in case of premature discontinuation). That means the sum of MBL values will be multiplied by {length of analysis period in units of days divided by 30 days}.

The cumulative volume of MBL at beginning of Year 6, end of Year 6, end of Year 7, and end of Year 8 of Mirena treatment will be presented by descriptive statistics. Furthermore, change from baseline (=beginning of Year 6) will be presented.

The basis for this analysis is the data on MBL assessed by the alkaline hematin method (see Integrated Protocol Section 9.4.2). If a women has sent in no sanitary products and has documented in the eDiary (see Integrated Protocol Section 9.7.1) that no bleeding occurred during one of the considered 30-day time periods for collection of sanitary protection, the MBL will be assumed to be zero in that time period.

This analysis will be conducted in the FAS in the HMB subgroup, i.e. women who had Mirena inserted for both contraception and HMB.

Sensitivity analysis approach #1 of MBL:

As described in Section 4.5, there might be cases when the MBL value remains missing. If such cases occur, a sensitivity analysis will be performed using (imputed) MBL values based on the extended imputation rules given in Section 4.5.

The cumulative volume of MBL will be calculated and summarized similarly as in the above primary analysis approach for MBL.

[figure not shown]

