6.2.2.2 Categorized menstrual blood loss (<80 mL / 30 days)

No clinical change in bleeding profile regarding HMB after Year 5 until the end of Year 6, until the end of Year 7 and until the end of Year 8, respectively, will be concluded if the cumulative volume of MBL was < 80mL at the beginning of Year 6 and remained remains <80mL during the end of years 6, 7 and 8, respectively. Vice versa, clinical change in bleeding profile regarding HMB after Year 5 until the end of Year 6, end of Year 7 and end of Year 8, respectively, will be concluded if the volume of blood loss was ≥ 80mL at the beginning of Year 6 or at end of Years 6, 7 or 8, respectively.

Therefore, the proportion of women with clinical change in bleeding profile regarding HMB will be analyzed. Descriptive statistics as well as 95% Clopper-Pearson confidence intervals will be provided.

For the analysis after Year 6, the proportion of women with clinical change in bleeding profile regarding HMB **after Year 5 until the end of Year 6** will be analyzed.

CCI
[Redacted text block]

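### The length adjustment for menstrual blood loss in SAP 6.2.2.1 is upside down: a collection period shorter than 30 days is scaled down instead of up

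*SAP*

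**What the plan says.** Women in the HMB subgroup collect sanitary products in four planned 30-day windows. SAP 6.2.2.1 then forms a cumulative volume for each woman and window. It adjusts for length when collection was early or late without a gap, or when the woman discontinued prematurely: "the sum of MBL values will be multiplied by {length of analysis period in units of days divided by 30 days".

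Four other provisions bear on this.

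- **Scale.** The categorised endpoint is a 30-day volume, as the heading of SAP 6.2.2.2 shows ("Categorized menstrual blood loss (<80 mL / 30 days").
- **Validity of short windows.** SAP 6.2.2.1 invalidates a truncated window "if there are less than 20 solid observations before the subject discontinued prematurely during a 30-day collection period". A window cut short after 20 or more solid observations can therefore still count.
- **Data outside the windows.** The same section states that "potential additional MBL data from sanitary products collected outside these planned 30-day collection periods will be excluded from the statistical analysis".
- **The parallel rule for diaries.** For a bleeding diary that ends early, SAP 4.4 says: "The correction factor is the length of the reference period divided by the length of the diary".

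The adjusted volume feeds the MBL summaries, the change from baseline and the 80 mL classification. Under Protocol 10.3.2.2, success on the classification requires fewer than 20% of HMB women with a clinical change, and also that "the upper limit of the corresponding 95% Clopper-Pearson confidence interval is equal to or less than 35" per cent.

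**The concern.** An adjustment meant to make short windows comparable with full ones should raise the sum. The written factor is below 1 whenever L is below 30, so a sum that is already low because days are missing is lowered again. Even a woman whose unadjusted sum has reached 80 mL can be pulled back under the cut-off.

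For shortened windows the error has one direction: it can remove clinical changes but never add them, so it can only help the success criterion. Truncation may also be related to the outcome, because the reasons for possible withdrawal in Protocol 6.4.1 include this: "Return of heavy menstrual bleeding, if it affects" the woman's well-being. The women with truncated windows may be those the endpoint is meant to detect.

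**Working it through.** **The SAP's own length correction (SAP 4.4).** 15 bleeding days recorded in 75 of 90 days: 15 × 90/75 = 18, which matches the SAP. The direction used in SAP 6.2.2.1 would give 15 × 75/90 = 12.5.

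**The MBL factor.** Let S be the sum over L days. The 30-day volume is S × 30/L and the written value is S × L/30. Their ratio is (L/30)².

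| L (days) | Factor as written, L/30 | Factor needed, 30/L | Written ÷ correct | Observed sum needed to reach 80 mL: as written (80 × 30/L) | Observed sum needed: correct (80 × L/30) | 30-day loss still read as <80 mL, up to 80 × (30/L)² |
|---|---|---|---|---|---|---|
| 20 | 0.667 | 1.500 | 0.44 | 120.0 mL | 53.3 mL | 180.0 mL |
| 25 | 0.833 | 1.200 | 0.69 | 96.0 mL | 66.7 mL | 115.2 mL |
| 28 | 0.933 | 1.071 | 0.87 | 85.7 mL | 74.7 mL | 91.8 mL |
| 30 | 1 | 1 | 1 | 80 mL | 80 mL | 80 mL |

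Examples: 60 mL in 20 days is 90 mL per 30 days but is recorded as 40 mL. 100 mL in 20 days is 150 mL per 30 days but is recorded as 66.7 mL, although the cut-off was passed on the raw sum.

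**How L falls below 30.** Gaps inside a window are imputed or invalidate it, so they do not shorten L. The visible route is discontinuation within a window, with L of 20 to 29. Early or late collection is also named as a trigger, but its definition in SAP 4.5 is redacted. Because data outside the planned windows are excluded, any effect for L above 30 depends on that redacted text.

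**How many women.** SAP 3 sets the subgroup target: "it is targeted that 10% of the women to be treated (i.e. 36 women out of 360"). Assume dropouts fall evenly over 1095 days. Ten days in each of four windows give L of 20 to 29, so the share is 40/1095.

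- Completion ratio 200/360 applied to 36 women: 36 × 160/360 = 16 dropouts; 16 × 40/1095 = 0.58 women.
- The 15% dropout in Protocol 10.4 read as yearly: 36 × (1 − 0.85³) = 13.9; expected 0.51.
- The 15% read as a total: 36 × 0.15 = 5.4; expected 0.20.

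**Effect on the success rule (exact Clopper-Pearson upper limits).** One woman matters only at the boundary.

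| Evaluable women | Largest number of changes that passes | Next number, fails |
|---|---|---|
| 36 (target) | 6: 32.8% | 7: 36.0% |
| 30 (assumed) | 5: 34.7% | 6: 38.6% |
| 25 (assumed) | 3: 31.2% | 4: 36.1% |
| 20 (assumed) | 2: 31.7% | 3: 37.9% |

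**The case against.** The case on the other side concerns reach, since no visible reading makes L/30 right.

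- **Redaction.** The terms for solid observations and for early or late collection are defined in redacted text. If the analysis period always meant 30 days, the factor would be 1, but the adjustment would then do nothing in the situations it is written for. The redaction limits what can be said about frequency; it does not rescue the formula. It does make L of 20 to 29 a widest case, since L = 20 is valid only if all 20 days are solid.
- **Rarity.** The 0.2 to 0.6 women are those with a shortened window, not those misclassified. Misclassification also needs a loss in the affected band, for which the documents give no prevalence. If 5% to 20% of them fell there (an assumption), the expected number misclassified would be 0.2 × 0.05 = 0.01 to 0.6 × 0.20 = 0.12. This stands. A subgroup below 36 would lower it further, and SAP 7 (v2.0 entry) already records low HMB numbers.
- **Denominator.** Under the denominator rules in Protocol 15.1.2.31, a woman without a recorded change and without the assessment at the analysis time point leaves the denominator. A woman misread in an earlier window would therefore leave both counts. At 36, 7/36 becomes 6/35 (33.6%) and the result still flips to a pass. At 30, 6/30 becomes 5/29 (35.8%) and still fails. At 25 and 20, 3/24 (32.4%) and 2/19 (33.1%) pass. This stands as a limit on the n = 30 row: that flip needs truncation in the window at the analysis time point itself.
- **Change from baseline.** A woman who discontinues in the baseline window has no later value, so only truncation in a later window affects this summary. This also stands.

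**Conclusion.** The formula is wrong as written. It is the reciprocal of what a 30-day volume requires, it runs against the SAP's own rule in Section 4.4, and the document history in SAP 7 lists no correction of it through v5.0. For any valid window shorter than 30 days the reported volume is (L/30)² of the correct one, and the bias favours success on the HMB criterion.

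The practical reach is small: a secondary endpoint, a subgroup of about 36, and probably fewer than one woman with a shortened window if dropout is even. Clustering of dropouts would change that count. One misread woman alters the conclusion only at the pass/fail boundary. The programs may already use the correct factor, but then they depart from the plan without a record. It should be fixed; confidence in the defect itself is high.

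**What to change.** In the next SAP supplement, state in Section 6.2.2.1 that the summed MBL is multiplied by 30 days divided by the number of days in the analysis period. Check which factor the derivation program uses, and record the answer. If it follows the written text, rerun MBL, change from baseline and categorised MBL for every shortened window, including those used in the Year 6 and Year 7 analyses. List the women whose class relative to 80 mL changes.

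The cost is one line of SAP text, one code check and, if needed, a rerun for a few windows. No new data are required.

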6.2.2.2 Categorized menstrual blood loss (<80 mL / 30 days)

No clinical change in bleeding profile regarding HMB after Year 5 until the end of Year 6, until the end of Year 7 and until the end of Year 8, respectively, will be concluded if the cumulative volume of MBL was < 80mL at the beginning of Year 6 and remained remains <80mL during the end of years 6, 7 and 8, respectively. Vice versa, clinical change in bleeding profile regarding HMB after Year 5 until the end of Year 6, end of Year 7 and end of Year 8, respectively, will be concluded if the volume of blood loss was ≥ 80mL at the beginning of Year 6 or at end of Years 6, 7 or 8, respectively.

Therefore, the proportion of women with clinical change in bleeding profile regarding HMB will be analyzed. Descriptive statistics as well as 95% Clopper-Pearson confidence intervals will be provided.

For the analysis after Year 6, the proportion of women with clinical change in bleeding profile regarding HMB **after Year 5 until the end of Year 6** will be analyzed.

CCI
[Redacted text block]

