8.1 Concomitant therapy

For the use of concomitant medications please refer to Section 6.2 (Exclusion criterion #14).

All medications taken during the study (i.e. starting with the date of informed consent) will be recorded in the eCRF using the trade name, indication, dose, unit, frequency, route of administration and dates of intake (i.e. start and stop dates).

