9.6.1.2.5 Other specific treatment(s) of adverse events

- None
- Remedial drug therapy
- Other

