9.6.1.3 Assessments and documentation of adverse events

The investigator has to record on the respective eCRF pages all adverse events occurring in the period between the signing of the informed consent and the end of study; after the end of the study there is no requirement to actively collect AEs including deaths. The type of information that should be assessed and recorded by the investigator for each AE is listed in Section 9.6.1.2.

“Death” should not be recorded as an AE on the AE page. Instead, “death” is the outcome of underlying AE(s).

For all serious adverse events (SAEs) the sponsor has to carry out a separate assessment for expectedness, seriousness and causal relationship to study drug.

The following events should **not be reported as AEs/SAEs**, unless (i) they are specifically considered as such by the investigator, according to the following conditions, or (ii) they lead to withdrawal of a subject from the study. This is to avoid redundancy and/or inconsistent reporting of AEs as these data may already be recorded in the CRF or subject’s eDiary.

- **Ovarian cysts:** An ovarian cyst should only be reported as an AE if it is felt to be non-physiologic (at the discretion of the investigator). Ultrasound examinations will not be routinely scheduled as part of this study but may be performed by the investigator if thought to be necessary to evaluate symptoms of an ovarian cyst or other pelvic pathology. If an ovarian cyst is diagnosed, follow-up should be in accordance with the investigator’s standard practice.

- **Findings on the bleeding diary:** Uterine bleeding (including intracyclic bleeding and absence of bleeding) should be recorded as an AE only if:
 - it leads to study discontinuation
 - it leads to therapeutic or diagnostic procedures
 - it is regarded as SAE
 - it shows a clinically significant worsening during the study that, in the judgment of the investigator, is not consistent with the expected clinical course, or are specifically reported as AEs by the subject.

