6.1.2.3 Previous and concomitant medications

All concomitant medications taken during the study (i.e. starting with the date of informed consent) as well as the extended use of Mirena (i.e. the study drug) with its date of insertion and indication at the time of insertion (contraception, or contraception plus HMB), will be recorded on the eCRF.

The extended use of Mirena (i.e. the study drug) will be summarized as described in Section 6.1.3, whereas all concomitant medications taken during the study (excluding the extended use of Mirena) will be summarized by World Health Organization (WHO) Drug Dictionary substance name.

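### The visible HMB success rule has no term for added bleeding treatment, so a woman kept below 80 mL in every assessed window by another drug counts as no clinical change

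*SAP*

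**What the plan says.** **The rule.** Under SAP 6.2.2.2 a clinical change "will be concluded if the volume of blood loss was ≥ 80mL at the beginning of Year 6" or at the end of Year 6, 7 or 8. The SAP's numerator and denominator lists are redacted. The new text in Protocol 15.1.2.31 (Amendment 1) shows them in full, and every item is a menstrual blood loss (MBL) item. The SAP history (Section 7) logs only a terminology correction to 6.2.2.2 after v1.0. Under Protocol 10.3.2.2, success is concluded "if less than 20% of the women in the HMB subgroup have a clinical change in bleeding profile regarding HMB" and the upper limit of the 95% Clopper-Pearson "confidence interval is equal to or less than 35" per cent.

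**Other treatment for bleeding.** Protocol 8.1 states: "For the use of concomitant medications please refer to Section 6.2 (Exclusion criterion #14"). That criterion covers other sex-hormone preparations. Among the reasons for which a subject may, not must, be withdrawn, Protocol 6.4.1 lists: "Return of heavy menstrual bleeding, if it affects the subject's well-being, based on the investigator's clinical judgment". Protocol 9.6.1.3 makes diary bleeding an adverse event if, among other conditions, "it leads to therapeutic or diagnostic procedures". Protocol 9.6.1.2.5 offers "Remedial drug therapy" as a treatment category for any adverse event.

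**What is done with the data.** Protocol 8.1 records each medication with its indication and its start and stop dates. SAP 6.1.2.3 says "all concomitant medications taken during the study (excluding the extended use of Mirena) will be summarized by World Health Organization (WHO) Drug Dictionary substance name". The one visible MBL sensitivity analysis (SAP 6.2.2.1) deals with missing values.

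**The concern.** Protocol 5 says the HMB subgroup is there to show that the effect on blood loss lasts through extended use. The study has no control arm, so a lower volume produced by an added drug cannot be separated from Mirena's own effect. If that drug keeps a woman below 80 mL, she enters the success statement as evidence for Mirena. The mechanism can lower the event count but never raise it, so any error favours success.

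The plan already accepts the principle for its primary endpoint. SAP 6.2.1 removes 28-day periods with backup contraception from Pearl Index exposure, because women using it are at lower risk of pregnancy. The HMB endpoint has no visible counterpart.

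**Working it through.** **1. Is there a plan figure to reproduce?** The visible text gives no sample size or power for the HMB rule; a redacted block follows the Pearl Index figures in Protocol 10.4. Those figures do reproduce. With 832 woman-years the upper limit is at most 1 if there are 2 or fewer pregnancies. The Poisson probability of that is 76.7% at mean 8.32 × 0.2 = 1.664 (stated 76%) and 54.5% at mean 8.32 × 0.3 = 2.496 (stated 55%). They do not bear on the HMB rule, so the rest starts from the rule itself.

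**2. How the visible rule treats each course**

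| Course of a woman with Mirena in place | Classification |
|---|---|
| Over the threshold in any window, then treated | Change, at that and every later analysis |
| Treated, but still over the threshold in a window | Change, likewise |
| Bleeding returns and is treated between windows; below 80 mL in every window | No change |
| Under treatment during a window; below 80 mL in every window | No change |

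Only the last two rows are the problem. The windows cover 4 × 30 = 120 days, and 120/1095 = 11.0% of the three years, so treatment between windows can pass unseen. (The amendment lists use >80 mL and the definition uses ≥80 mL; this does not affect the point.)

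**3. Where the rule passes.** Inputs: the criteria <20% and ≤35% (Protocol 10.3.2.2) and the target of 36 women (Protocol 5). An assumed 20 evaluable women at Year 8 comes from applying the overall completion target: 36 × 200/360 = 20. With x events in n women, the upper limit is the 0.975 quantile of Beta(x+1, n−x).

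| n | Most events that pass | Upper limit | One more event | Upper limit |
|---|---|---|---|---|
| 36 | 6 (16.7%) | 32.8% | 7 (19.4%) | 36.0% |
| 30 | 5 (16.7%) | 34.7% | 6 (20.0%) | 38.6% |
| 25 | 3 (12.0%) | 31.2% | 4 (16.0%) | 36.1% |
| 20 | 2 (10.0%) | 31.7% | 3 (15.0%) | 37.9% |

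The smaller rows matter because the SAP v2.0 history entry remarks that the subgroup is small.

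**4. Women needed to reverse a pass.** At n = 36 failure needs 7 events. From 6 measured changes it takes 1 reclassified woman, from 5 it takes 2, from 4 it takes 3, and from 0 it takes 7. At n = 20 failure needs 3 events: 1 woman from 2, 2 from 1, 3 from 0.

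**5. Illustration with assumed rates.** The documents give no treated share. Suppose 10% of women have a measured change and a further share t are treated and below 80 mL in every window. If treated women count as a change, P(success) = P(X ≤ 6) with X ~ Bin(36, 0.10 + t), or P(X ≤ 2) with X ~ Bin(20, 0.10 + t).

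| t | 0% | 3% | 5% | 10% | 15% |
|---|---|---|---|---|---|
| n = 36 | 93.7% | 82.0% | 71.0% | 40.1% | 16.8% |
| n = 20 | 67.7% | 50.8% | 40.5% | 20.6% | 9.1% |

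Under the visible rule the probability stays in the t = 0 column whatever t is.

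**The case against.** The strongest reply is that the objective is to assess blood loss and the variable is a volume. Analysing the measured volume whatever else is taken is a recognised strategy, and counting treatment as an event turns the variable into a composite. That is fair, and it is why the remedy is a sensitivity analysis and not a new main rule. It does not remove the gap: the visible text does not state that choice, and the stated purpose is to show that the effect is maintained.

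Other points stand in part:
- **Redaction.** SAP 6.2.2.1 numbers its visible MBL sensitivity analysis as the first approach, and parts of 4.5 and 6.2.2.2 are blacked out. A further analysis may be hidden. The amendment lists and the SAP history make a hidden medication term in the main rule unlikely, but they say nothing about hidden sensitivity analyses.
- **Discretionary safeguards.** Exclusion criterion 17 and the withdrawal rules let the investigator act when a condition arising on study conflicts with the objectives. Anticoagulant use is an optional withdrawal reason, and backup contraception is limited to barrier methods. None of these restricts non-hormonal treatment of bleeding.
- **Small numbers.** The sensitivity to one woman comes from the small subgroup and would arise with any misclassification. Here, though, the direction is known.

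A reader might infer that every woman whose heavy bleeding returns and is treated is counted as a success. The documents do not support that: the numerator is cumulative, so loss above the threshold in any window makes her an event from then on. Nor do they show that the protocol expects returned heavy bleeding to be treated with Mirena in place. The adverse-event category is generic, and the bleeding condition also covers intracyclic bleeding.

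**Conclusion.** The point holds in limited form. On the visible text, a woman given non-hormonal drug treatment for heavy or increased bleeding while Mirena stays in place, and below 80 mL in every assessed window, counts as no clinical change. In an uncontrolled subgroup this can only favour success.

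Its size is unknown, because the number of such women is not in the documents. One woman decides the result only at the margin (6 of 36, or 2 of 20), and well inside it the conclusion is robust. The figures rest on the target of 36, the assumed 20 evaluable women, and assumed treated shares of 0 to 15%. The documents do not support saying that the HMB conclusion would be wrong, or that no further sensitivity analysis exists. This should be corrected, with medium confidence.

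**What to change.** In SAP 6.2.2.2, keep the MBL rule and add a pre-specified sensitivity analysis, reported beside the success statement and judged against the same <20% and ≤35% criteria. In it, a woman is also placed in the numerator and denominator as a clinical change if both of the following hold:
- the eCRF records drug or procedural treatment whose indication is heavy or increased uterine bleeding, not intracyclic bleeding or spotting;
- the treatment was given at any time from the baseline visit, or was ongoing at that visit, to the end of the collection window for the analysis in question.

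Starting at the baseline visit matters. Baseline collection runs over study days 2 to 31, and the visit may fall up to 14 days before the end of Year 5, so a start at Day 1 of Year 6 could miss treatment during that window.

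For the continuous MBL summary in SAP 6.2.2.1, repeat the analysis with collection windows that overlap such treatment excluded.

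The cost is one extra derivation and a possibly less favourable proportion. One short course makes a woman an event for all later analyses, so this version is deliberately conservative. Medication indications and dates are already collected, and earlier SAP supplements have added analyses. No change to patient care is proposed.
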